Secondary outcomes will be assessed at all major time points. Since HOPE is associated with significant decreases in depression (see C1) and PTSD and depression frequently co-occur⁵⁹, depression will be assessed with the **Center for Epidemiological Studies Depression Scale (CESD⁶⁰)**. Additionally, given the established relationships between IPV and child abuse and maltreatment²² and mental health symptoms and child abuse potential in victims of IPV living in shelters⁴², we will also assess participants' child abuse potential with the brief form of the **Child Abuse Potential Inventory (CAPI⁶¹)**. The brief CAPI is a well validated and frequently employed measure that assesses 7 known correlates of child abuse (i.e., distress, family conflict, rigidity, happiness, feelings of persecution, loneliness, financial insecurity) without directly assessing violence towards children, making the measure acceptable to parents. The impact on quality of life (as both a secondary outcome and for cost analyses described in C3) will be assessed using the **Veterans SF-12 (VR-12)** (the U.S. government's public use variant of the SF-12)⁶². Our prior work found the VR12 discriminates well between the quality of life losses associated with different levels of PTSD⁶³. This research also found that Sengupta's HUI3 scoring⁶⁴ was the best of 50 existing scorings of the VR-12. That scoring measures functional status in quality-adjusted life years (QALYs), the quality of life measure routinely used in clinical trials of pharmaceuticals. Additionally, given that HOPE adopts an empowerment approach and a primary treatment goal is to increase participants' effective use of personal and social resources, the **Personal Progress Scale Revised (PPS-R)⁶⁵** will be used to assess empowerment, the **Social Support Questionnaire (SSQ⁶⁶)** will be used to assess degree and quality of social support, and the **Effectiveness in Obtaining Resources (EOR) Scale⁶⁷** will be used to assess perceived effectiveness in accessing community and shelter resources. Finally, as HOPE is a CBT that targets dysfunctional cognitions, the **Posttraumatic Cognitions Inventory (PTCI)⁶⁸** will be used to assess trauma-relevant cognitions.

Objective Measures of Stress Responding will be assessed at baseline, post-treatment, and 1-yr follow-up:

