The cost effectiveness analysis (CEA) measure will be cost/QALY gained, computed as [intervention cost minus direct cost savings]/QALYs saved. We will follow widely accepted CEA guidelines^{78,79}, including computing estimates from societal and government perspectives, adjusting future costs to present value with a 3% discount rate, and analyzing how sensitive the results are to higher and lower discount rates. Most intervention costs will be tracked in the project accounting system. The exception is the cost of social services with PCT versus HOPE. To estimate these costs, we will track the number of visits by type of service, then price those visits using average service prices. We are not powered to and will not try to track medical costs, especially since some domestic violence injuries can have lasting medical consequences. Instead, we will use our existing violent injury cost model⁸⁰⁻⁸³ and sexual violence costs⁸⁴ to cost each injury type tracked in our CTS data, then sum and compare the estimated costs of the injuries in the control versus the treatment groups. We will rely on published costs of depression by severity^{85,86} to compute the savings from reduced depression. These sources include direct medical and mental health care costs, as well as long-term QALY losses and life table effects. The evaluation data will record short-term employment impacts. The QALY measures partially incorporate those impacts so we will take care not to double count. Following guidelines,^{78,87} we will count employer savings due to reduced presenteeism of employed people who reduced their depression through HOPE as direct costs, using presenteeism impacts from Stewart⁸⁸. Using Oracle's Crystal Ball Excel add-in, we will enter uncertainty ranges for all parameters in the cost/QALY calculation. From that information, we will develop a Cost-Acceptability Curve that determines the probability that HOPE is preferred to standard care as a function of the value of a QALY. One third of all cost/QALY analyses now take this approach to uncertainty analysis⁸⁹ and we have guidelines exist on how to interpret the results.

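### The cost-acceptability curve is built from per-parameter uncertainty ranges, with no provision for the correlation between trial-measured costs and QALYs from the same women

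*Combined protocol and SAP*

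**What the plan says.** The cost-effectiveness paragraph of section C3 defines the measure as cost per QALY gained, "computed as [intervention cost minus direct cost savings]/QALYs saved". The inputs come from several places:

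- **Intervention cost:** "Most intervention costs will be tracked in the project accounting system".
- **Social services:** "we will track the number of visits by type of service, then price those visits using average service prices".
- **Injuries:** an existing outside cost model is applied to the trial's CTS data, and the plan will "then sum and compare the estimated costs of the injuries in the control versus the treatment groups".
- **Depression and presenteeism:** published values are applied to depression reduction.
- **QALYs:** section C2 (secondary outcomes) takes these from the VR-12 with an HUI3 scoring. C3 adds that the outside sources also carry long-term QALY losses.

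Table 1 schedules the VR-12, the CESD (depression) and the LIFE (service use) at the same six primary time points, and the CTS-2 at all ten.

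On uncertainty, the plan says "we will enter uncertainty ranges for all parameters in the cost/QALY calculation. From that information, we will develop a Cost-Acceptability Curve", and that the curve "determines the probability that HOPE is preferred to standard care as a function of the value of a QALY". It also plans discount-rate sensitivity analyses and estimates from two perspectives. C3 mentions no correlation, joint distribution or resampling of women for this analysis. Bootstrapping appears only in the mediation paragraph.

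**The concern.** A range describes one parameter at a time. The arm difference in VR-12 QALYs and the arm differences in priced injuries, depression and service use are estimated on the same women, so their sampling errors are related. A woman with less depression or fewer injuries will tend both to cost less and to score better on the VR-12. If the VR-12 QALY gain and the priced savings enter the spreadsheet as separate inputs, each with its own range, the simulation has nothing from which to recover that relation.

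The plan recognizes the overlap for the point estimates, since it undertakes not to count employment effects twice. It takes no matching step for the uncertainty. What is at stake is the curve, which is the only probability statement planned for cost-effectiveness. The closing aim in section D is to present HOPE as a cost-effective model program.

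**Working it through.** **Inputs from the documents.** They give the form of the ratio, the data sources and the simulation method. They give no curve reading, correlation, SD of cost or QALYs, or value of a QALY. There is therefore no plan figure to reproduce, and the sizes below rest on stated assumptions.

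**Step 1. Net benefit.** Let dE be the arm difference in QALYs, dC the arm difference in net cost, L the value of a QALY and rho the correlation of dE with dC. Then

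INB = L × dE - dC

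Var(INB) = L² Var(dE) + Var(dC) - 2 L Cov(dE, dC).

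Independent draws omit the last term.

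**Step 2. Ratio of variances.** With k = L × SE(dE) / SE(dC),

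Var(joint) / Var(independent) = 1 - 2 rho k / (1 + k²).

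The factor k / (1 + k²) is largest at k = 1, so equal contributions are the worst case for any given rho. Because k rises with L, the distortion varies along the curve.

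**Step 3. Effect on a reading.** Assume approximate normality, and that the means and the separate range widths are right. If independent draws show P, the joint value is

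Phi( z(P) / sqrt(1 - 2 rho k / (1 + k²)) ).

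**Step 4. Worked case, P = .90, z = 1.2816.**

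- k = 1, rho = -.5: ratio = 1 + .5 = 1.5; 1.2816 / 1.2247 = 1.046; Phi = .852. The standard error is understated by 1 - sqrt(1/1.5) = 18%.
- k = 1, rho = +.5: ratio = 1 - .5 = .5; 1.2816 / .7071 = 1.812; Phi = .965.
- k = 4, rho = -.5: ratio = 1 + 4/17 = 1.235; 1.2816 / 1.1114 = 1.153; Phi = .876.
- k = 4, rho = +.5: ratio = 1 - 4/17 = .765; 1.2816 / .8745 = 1.466; Phi = .929.

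k = .25 gives the same results as k = 4.

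**Step 5. Other readings.**

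| Reading with independent draws | k = 1, rho = -.5 | k = 1, rho = +.5 | k = 4, rho = -.5 | k = 4, rho = +.5 |
|---|---|---|---|---|
| .20 | .246 | .117 | .224 | .168 |
| .70 | .666 | .771 | .681 | .726 |
| .80 | .754 | .883 | .776 | .832 |
| .90 | .852 | .965 | .876 | .929 |
| .95 | .910 | .990 | .931 | .970 |

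At k = 1 and rho = -.3 the .90 reading becomes .869. The shift goes to zero as the reading approaches .50, and below .50 a negative rho moves the probability up.

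**Step 6. Simulation check.** With 400,000 draws at k = 1, separate draws gave .900. Letting one common draw feed both savings and QALYs, so that rho = -.5, gave .853, which agrees with the formula. It also shows that a shared input in the spreadsheet does carry dependence.

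**The case against.** The strongest reply is that the plan is silent on dependence and does not assert independence. A reader might infer that the plan samples cost and QALYs independently and throws their correlation away. The text does not say so. Independent inputs also need not give independent outputs: if one drawn input, such as a change in depression, feeds both savings and QALYs, dependence arises by itself. The outside sources named in C3 carry both costs and QALY losses, so this may happen for part of the model. That stands, but it is partial. Trial QALYs come from the VR-12 and depression savings from published costs by severity. As separate inputs they stay uncorrelated unless a correlation is entered, and none is planned.

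A reader might also infer that all costs come from the women's own data. They do not. Most intervention costs come from project accounts, medical costs are not tracked, and unit values come from outside. Uncertainty in those inputs has no within-woman correlation and dilutes the effect. This also stands.

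The sign is open too. HOPE aims to increase the use of resources, and service visits count as cost, so women who engage more could have both higher cost and more QALYs. That would make the correlation positive.

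Finally, this is a non-primary analysis, and C3 commits to CEA guidelines whose content cannot be checked here. That limits the importance of the point, but the gap in the written method remains.

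**Conclusion.** The point holds as a minor one about the choice of analysis. The stated method is ranges by parameter and a curve developed from them. It has no means of carrying the sampling correlation between VR-12 QALYs and the priced injuries, depression savings and service visits of the same women, except where a common drawn input happens to feed both sides. The variance of net benefit is then misstated.

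A reader might conclude that the curve will be too extreme, or too favorable to HOPE. The documents do not support that as a general result. It needs a negative cost-QALY correlation, and favorable to HOPE also needs a reading above 50%. The negative sign is plausible from the plan's own reasoning, but no estimate is given, and with a positive correlation the curve is too close to 50%. Nor is any figure in the plan wrong, since it states no probability.

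Under the assumed correlations of ±.5, a reading of .90 shifts by about 5 points down or 6.5 up at worst, and by 2 to 3 points either way when one term dominates four to one. Dilution by outside unit values would reduce this further.

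**What to change.** Add wording to the cost-effectiveness paragraph of C3, before outcome data are analyzed, that does the following:

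1. For inputs measured in the trial (CTS-2 injuries, depression savings, service visits, VR-12 QALYs), resample women with replacement within each arm, keeping each woman's costs and QALYs together.
2. Use the resulting pairs of arm differences as the joint draws in the simulation.
3. Keep separate distributions for outside unit values. Where one outside source feeds both costs and QALYs, use a single common draw for both.
4. Build the curve from these draws.

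The bootstrap draws describe HOPE against PCT, the randomized comparator, whereas the curve sentence names standard care. That is a separate matter, but the same edit should make the comparator explicit.

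The cost is a little more analysis work, including combining the resampling with the multiple imputation already planned. No new data are needed. The stated probability that HOPE is preferred may move in either direction.

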
Drs. [name] and [name] have previously collaborated in a study investigating salivary cortisol levels in IPV victims⁴⁵. Using similar methodology as proposed here in which 4 salivary samples were collected over a 1-hour period (see C2), the cortisol awakening response was investigated in a sample of 52 shelter residents. Results suggested that IPV-related PTSD severity was associated with significantly greater cortisol output the first hour after waking. Thus, pilot data support the use of cortisol response within S-IPV victims as well as the ability of the research team to successfully collect multiple saliva samples from shelter residents.

C2. Study Design: To test our hypotheses that HOPE will significantly reduce severity of IPV-related PTSD and re-abuse in S-IPV victims compared to PCT, we plan to enroll 186 residents of battered women shelters with IPV-related PTSD into a prospective randomized controlled trial comparing HOPE to a attention-matched control condition (i.e., PCT). Residents of battered women shelters meeting study eligibility (see below) will be randomized into one of the two study arms. Participants will be offered 16 sessions of therapy (see Figure 1), either HOPE or PCT, beginning while women are in shelter (0-10 sessions) and continuing until 3-months post-shelter (6-16 sessions). The number of sessions attended within the shelter environment is dependent on participants' length of shelter stay, with a maximum of 10 sessions in shelter. Participants will then complete the remaining 6-16 sessions of HOPE outside of shelter. Therapy sessions will occur in shelter or another convenient, safe, and confidential location. Participants will be blinded to whether or not they received the investigative treatment or control condition. Blinded outcome assessments will be administered 1-week post-shelter treatment, 1-week post-shelter, and 1-week, 6-months, and 1-year-post-treatment.

Figure 1. Proposed model for delivery of treatment and assessment of outcome.

*Participants who are still in shelter after their 10th session will participate in monthly booster sessions.

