Rationale for the study design: Pilot work with HOPE has determined that HOPE is associated with improved outcomes relative to standard shelter services alone. Given that there is no other existing PTSD treatment appropriate for this population that could serve as a comparison condition the next logical stage in evaluating the efficacy of HOPE is to determine if HOPE offers improvement over a credible control condition that controls for the nonspecific components of therapy. PCT (see appendix) is a problem-focused, supportive therapy that is frequently used as an attention-matched control condition in clinical trials of PTSD^{46, 47}. PCT does not incorporate any of the hypothesized active ingredients of HOPE (e.g., cognitive-restructuring, acquisition of new behavioral skills, safety planning, access to resources, and empowerment strategies), but does provide psychoeducation on PTSD. Further, PCT is also clinically realistic, as many practitioners incorporate this approach into their standard practice⁴⁸. Therefore, we chose to compare HOPE to PCT, in order to determine if components specific to HOPE are responsible for observed effects, rather than nonspecific factors consistent with supportive therapy. [name] who has established expertise in PCT⁴⁶ will assist in adapting PCT to meet the needs of the proposed study, as well as in the training and supervision procedures for the PCT arm of this study.

Sample and recruitment: Participants will be 186 women recruited over 27 months from six battered women's shelters in five different counties within a 55 mile radius of the University of Akron (see letters of support) and randomized either to receive HOPE ($n = 93$) or PCT ($n = 93$). Both treatments will start while women are residents of shelter and extend after they leave shelter. Given that the length of shelter stay is variable and outside of experimenter control, session frequency will be individualized based on length of shelter stay. We are currently employing this model in our work with HOPE with success (see C1). Participants in both treatment conditions will receive up to ten individual sessions while in shelter, and 16 sessions in for up

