LIFE	X		X	X		X		X		X
CSQ						X		X		X

Note. MSSSI administered at any time point if participant endorses SI. CAPS administered at mid-tx assessments if DTS increases 50%. *Only the substance module of SCID-I/P administered at follow-up.

Adherence and Competence: All therapy sessions will be recorded. [name], a consultant on this project who is well-trained in treatment of IPV-related PTSD, as well as in HOPE, serving as a therapist in our pilot work with HOPE will rate adherence and competence of the delivery of 5% of randomly selected HOPE and PCT sessions (i.e., 74 HOPE and 74 PCT sessions). She will also participate in the PCT training with the study therapists and consult with [name] in order to develop competence in rating PCT sessions. HOPE and PCT have established adherence and competence scales used in prior research (see appendix)^{37, 46}.

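### The cost-acceptability curve is planned against standard care, but the trial's only comparator is PCT, and the cost/QALY formula does not say whether PCT cost is subtracted

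*Combined protocol and SAP*

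**What the plan says.** The cost-effectiveness paragraph in C3 (Data Analytic Plan) sets the measure as cost per QALY gained: intervention cost less direct cost savings, divided by QALYs saved. Uncertainty ranges are to be entered for all parameters, and from these a Cost-Acceptability Curve is derived that "determines the probability that HOPE is preferred to standard care as a function of the value of a QALY".

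The same paragraph names other groups when it describes its inputs. Most intervention costs come from project accounting. "The exception is the cost of social services with PCT versus HOPE", and that cost is to be estimated from visit counts and average prices. Injury costs are summed and compared between the control and treatment groups.

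The design has no third group. Under Study Design in C2, eligible residents "will be randomized into one of the two study arms", and "Participants will be offered 16 sessions of therapy (see Figure 1), either HOPE or PCT". Sample and recruitment gives 93 women per arm. The design rationale in C2 places standard shelter services in the past: pilot work determined that "HOPE is associated with improved outcomes relative to standard shelter services alone", and this trial moves on to an attention-matched control.

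**The concern.** A cost-acceptability curve is a statement about one contrast. Its incremental cost and incremental QALYs must come from the same two options, and those must be the options named in the conclusion. Here the named option is standard care, while the trial supplies HOPE and PCT. An analyst following the text would report a probability that the data do not estimate.

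The formula adds a second difficulty. It does not say whether intervention cost means the full cost of HOPE or HOPE net of PCT. With standard care as the named comparator, the full cost of HOPE could be entered against savings and QALYs measured relative to PCT.

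The stake is how the economic result is used. The document closes with the aim of packaging HOPE as a cost-effective model program for wide use. A shelter or funder would take a comparison with standard care to mean a comparison with what it provides now.

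**Working it through.** **Step 1: which comparator each part of the plan uses.**
- Curve (C3, cost-effectiveness paragraph): standard care.
- Social-service costs (same paragraph): PCT versus HOPE.
- Injury costs (same paragraph): control versus treatment group.
- Randomized arms (C2, Study Design; Sample and recruitment): HOPE, n = 93, and PCT, n = 93.
- Standard shelter care or services (C1, Initial Efficacy; C2, design rationale): the pilot comparator.
- External sources in C3 (injury and sexual-violence cost models, published depression costs and QALY losses, presenteeism impacts, average service prices): these put values on outcomes. None describes the costs or QALYs of women under standard care.

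Only the curve refers to standard care, and nothing in the paragraph feeds it.

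**Step 2: planned therapy volume.** Planned sessions per arm are 93 × 16 = 1,488. The plan's own figure confirms this for both arms: the Adherence and Competence section rates 5% of sessions, stated as 74 HOPE and 74 PCT, and 0.05 × 1,488 = 74.4. Sixteen is the number offered, not attended. Sample and recruitment words the post-shelter count differently, but that does not affect the comparator question.

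**Step 3: what the formula could mean.** Write C for delivery cost per woman, S for direct savings and Q for QALYs, with H = HOPE, P = PCT and U = standard care. ΔS and ΔQ are HOPE minus the stated comparator.
- (a) HOPE versus PCT throughout: [(C_H − C_P) − ΔS_HP] / ΔQ_HP.
- (b) HOPE versus standard care throughout: [(C_H − C_U) − ΔS_HU] / ΔQ_HU.
- (c) Mixed: [C_H − ΔS_HP] / ΔQ_HP.

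The trial can estimate (a). It cannot estimate (b), because C_U, ΔS_HU and ΔQ_HU have no stated source. Reading (c) is open to an analyst because the formula does not define intervention cost. The numerators of (c) and (a) differ by exactly C_P.

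In planned sessions, (a) carries 1,488 − 1,488 = 0 incremental sessions and (c) carries 1,488, or 16 per woman. For (b), the figure is 16 per woman less whatever therapy women receive under standard care, which the documents do not give.

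**Step 4: money and QALYs.** The documents state no cost per session, no PCT delivery cost and no expected QALY difference. The shift in the ratio or the curve cannot be calculated.

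**The case against.** The strongest reply is that standard care is a slip for the control arm. The paragraph elsewhere contrasts PCT with HOPE, the curve is built from those inputs, and the design rationale calls PCT clinically realistic because many practitioners work this way. As an account of how the wording arose, that is plausible. It does not make the term right. The document never calls PCT standard care, defines it as an attention-matched control that must be adapted for this study, and separates it from the shelter services used as the pilot comparator. The slip reading also leaves the undefined numerator untouched.

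Other parts of the reply stand:
- The document does not define standard care. A reader might infer that it means no therapy, so that the whole cost of HOPE is incremental to it. The documents do not support that. Pilot controls were referred to community treatment; 60% did not follow up while in shelter, so up to 100 − 60 = 40% may have done so.
- A reader might infer that incremental cost is understated by a definite amount. That would need PCT cost to be subtracted, which the formula does not say, together with a session price and PCT attendance, which the documents do not give. The pilot mean of 12.7 sessions is for HOPE.
- The curve is not presented as the main economic result. The stated measure is cost per QALY, and the curve expresses its uncertainty.

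**Conclusion.** The point holds as a mismatch between the comparator named for the curve and the only comparator in the trial, together with a numerator that does not fix the contrast. As written, the curve cannot support a conclusion against standard care, and two comparators could be mixed in one ratio.

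The size is known only structurally: the consistent and mixed numerators differ by the full delivery cost of PCT, which is 16 planned sessions per woman. Neither the size nor the direction of error in a claim against standard care can be given, because the QALY gain would refer to a different contrast too. The finding rests on one assumption: that no standard-care costs or QALYs enter from a source the plan does not mention.

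A reader might infer that the efficacy conclusions are also weakened. They are not. Randomization, the primary outcomes and the sample size of 186 do not depend on this paragraph.

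**What to change.** In the cost-effectiveness paragraph of C3:
1. Name PCT as the comparator for both the cost/QALY ratio and the Cost-Acceptability Curve.
2. Define intervention cost as HOPE cost minus PCT cost, so that costs, savings and QALYs share one contrast. Confirm that project accounting will record delivery costs separately by arm; the plan does not say.
3. If a comparison with standard care is wanted, present it as a separately labelled model-based scenario, with the external sources for its costs and QALYs stated and their uncertainty carried through.

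The first two are wording changes, plus a check on the accounting set-up. They need no additional participants or assessments. The cost is a narrower conclusion: the trial-based result would say whether HOPE is good value relative to PCT, not relative to what shelters now provide. The third takes extra modelling work and is optional.
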